Rationnel et Objectifs	
Le cytochrome P450 2C19 (CYP2C19) est l'enzyme responsable du métabolisme de médicaments fréquemment prescrits en clinique comme l'oméprazole, un antiacide inhibiteur de la pompe à proton (IPP), le citalopram, un antidépresseur inhibiteur sélectif de la recapture de la sérotonine (ISRS) ou le clopidogrel, un antiagrégant plaquettaire. Le CYP2C19 présente une importante variabilité interindividuelle de son activité dans la population générale due, notamment, à un fort polymorphisme génétique, avec une trentaine de variants alléliques identifiés à ce jour. Ceci résulte en cinq phénotypes distincts dans son activité : le phénotype métaboliseur lent (PM), le phénotype métaboliseur intermédiaire (IM), le phénotype métaboliseur normal (NM), le phénotype métaboliseur rapide (RM) et le phénotype métaboliseur ultra-rapide (UM).
 
Pour caractériser l'activité du CYP2C19, il existe différentes méthodes de phénotypage à savoir l'administration d'une substance-test métabolisée de manière spécifique par le CYP2C19 et la mesure de paramètres pharmacocinétiques, tels que l'aire sous la courbe (AUC), ou des ratios métaboliques entre les concentrations de la molécule-mère et de son métabolite. Les substances-tests les plus utilisées sont l'oméprazole (OPZ) et la méthénytoïne. Il est également possible de mesurer le phénotype de plusieurs isoformes des CYPs simultanément avec le phénotypage mixte, tel que le « Geneva cocktail » développé aux HUG. Ce dernier est composé de 6 substances-tests permettant de phénotyper simultanément 6 isoformes des CYPs, dont l'OPZ pour le CYP2C19.
 
Malgré une bonne tolérance de ce cocktail, certains patients peuvent être réticents à l'administration de médicaments de manière exogène et il n'est parfois pas possible de les administrer à certains patients (e.g. femmes enceintes, enfants, personnes âgées). Il convient par ailleurs d'attendre 2h après l'ingestion du « Geneva cocktail » avant d'effectuer la prise de sang, ce qui peut poser quelques contraintes pratiques en clinique.
 
L'utilisation de biomarqueurs endogènes de mesure de l'activité des CYPs permettrait ainsi de s'affranchir de ces obstacles et de rendre la pratique moins invasive et plus acceptable pour les patients. Une récente étude consacrée au CYP2D6 conduite au sein de notre service a permis d'identifier de nouveaux biomarqueurs endogènes pour cet isoforme, à savoir la solanidine, un alcaloïde aglycone très commun, et ses dérivés.
 
Le but de notre étude est d'identifier de nouveaux biomarqueurs endogènes pour mesurer (phénotyper) l'activité du CYP2C19 par métabolomique non ciblée.
 
Les volontaires sains seront stratifiés en deux groupes selon leur phénotype pour le CYP2C19 : les sujets PMs et NM-RMs-UMs. Les sujets IMs seront exclus afin d'observer des différences plus significatives au sein des deux groupes.
 
Objectif primaire :
 
 - Partie 1 : mise en évidence de potentiels substrats et/ou métabolites endogènes du CYP2C19 par métabolomique non ciblée sur des échantillons urinaires, plasmatiques et de vésicules extracellulaires dérivées du foie prélevés avant (baseline, session 1) et après administration répétée de fluvoxamine (inhibition enzymatique du CYP2C19, session 2) ainsi qu'après administration répétée de rifampicine (induction enzymatique du CYP2C19, session 3). - Partie 2 : identification des substrats et/ou métabolites endogènes du CYP2C19 parmi les composés mis en évidence dans la partie 1 par analyse semi-quantitative ciblée sur des échantillons urinaires, plasmatiques et de vésicules extracellulaires dérivées du foie des volontaires sains PMs et NM-RMs-UMs à la baseline (i.e sans administration préalable de fluvoxamine ou de rifampicine). 
Objectifs secondaires :
 
 - Identification des substrats et/ou des métabolites endogènes du CYP2C19 à l'aide de bases de données internes ou externes, par fragmentation en LC-MS/MS ou à l'aide de standards de référence. - Corrélation des concentrations plasmatiques et/ou urinaires et/ou de vésicules extracellulaires dérivées du foie d'un substrat et/ou un métabolite endogène du CYP2C19 avec le phénotype (ratio sanguin OH-oméprazole/oméprazole) et/ou le génotype du CYP2C19.

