Méthode	
Le projet consiste en trois parties expérimentales :
 
 - Partie 1 : mesure de l'impact d'un inhibiteur du CYP2C19, la fluvoxamine, sur le métabolome urinaire, plasmatique et de vésicules extracellulaires dérivées du foie - Partie 2 : mesure de l'impact d'un inducteur du CYP2C19, la rifampicine, sur le métabolome urinaire, plasmatique et de vésicules extracellulaires dérivées du foie - Partie 3 : mise en évidence des biomarqueurs du CYP2C19 par mesure de l'impact des polymorphismes du CYP2C19 sur les composés affectés dans les parties 1 et 2. 
Il s'agit d'une étude ouverte à design croisé chez des volontaires sains répartis en deux groupes selon leur génotype du CYP2C19 (PMs et NMs-RMs-UMs). Trois sessions auront lieu pour chaque sujet :
 
Session 1 : prélèvements plasmatique et urinaire ainsi que la détermination du ratio sanguin OH-oméprazole/oméprazole à la baseline par prise de sang capillaire.
 
Session 2 : idem session 1 avec prise au préalable de 50 mg de fluvoxamine pendant 7 jours consécutifs (inhibiteur fort du CYP2C19).
 
Session 3 : idem session 1 avec prise au préalable de 600 mg de rifampicine pendant 10 jours consécutifs (inducteur fort du CYP2C19).
 
A chaque session, une récolte urinaire sur 24h est effectuée, suivie d'une prise de sang veineux (6 x 6 ml) le matin à jeun. Le phénotypage a ensuite lieu avec la prise d'oméprazole à 10 mg, suivie d'une prise de sang capillaire (4 x 10 µl) après 2h. Après la session 1, la prise de fluvoxamine a lieu durant 7 jours consécutifs (administration au total de 7 doses de fluvoxamine à 50 mg), pouvant commencer au moment du repas de midi lors du déroulement de la session 1. La dernière prise de fluvoxamine doit avoir lieu 2h avant l'administration d'oméprazole à 10 mg lors de la troisième visite (jour 11±4j, session 2). Enfin, la prise de rifampicine aura lieu au moins 6 jours après la session 2, tous les soirs durant 10 jours consécutifs (administration au total de 10 doses de rifampicine à 600 mg). La dernière prise de rifampicine doit avoir lieu le soir de la veille de l'administration d'oméprazole à 10 mg lors de la quatrième visite (jour 27±4j, session 3).

Nombre de volontaires	40 volontaires sains : 10 PMs et 30 NMs-RMs-UMs
Durée de l'étude	Au minimum 24 jours et au maximum 32 jours par volontaire

[figure not shown]

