Critères de sélection	
Critères d'inclusion :
 
Hommes et femmes en bonne santé habituelle Age : entre 18 et 65 ans IMC : entre 18 et 27 Capables de donner leur consentement éclairé Compréhension de la langue française Génotype du CYP2C19 : PMs, NM_s, RM_s ou UM_s Au moins une contraception à effet barrière pendant toute la durée de l'étude et 1 mois après la fin de l'étude (en plus de la contraception hormonale habituelle le cas échéant)
 
Critères de non-inclusion :
 
Génotypes IM_s du CYP2C19 Participation à un autre essai clinique interventionnel dans les 3 mois précédent l'inclusion Femme enceinte ou allaitante Pathologies, médicaments ou aliments qui affectent l'activité des CYP450 Antécédent de transplantation hépatique Fumeurs réguliers de ≥ 10 cigarettes/jour Altération des tests hépatiques (ASAT, ALAT, GGT, bilirubine plus de 3x la norme) Insuffisance rénale (urée sérique, créatinine sérique et eGFR en dehors des normes) Antécédent d'alcoolisme chronique ou d'abus de substances psychotropes Allergie aux médicaments administrés Pathologie psychiatrique active Score de Beck ≥ 10 (question sur le suicide > 0) Prise d'alcool 2 jours avant la session 1 et pendant la prise de fluvoxamine et rifampicine Porteurs de lentilles de contact

Produit d'étude Dosage Voie d'administration Durée du traitement	
Oméprazole Spécialité : Antramups® Dosage : prise unique d'un comprimé de 10 mg d'Antramups® le matin à chaque session de phénotypage Voie d'administration : orale Durée de traitement : prise unique, à chaque session Dose thérapeutique habituelle : 20-40 mg/j, selon l'indication
 
Fluvoxamine Spécialité : Floxyfral® junior cpr pell 50 mg Dosage : un comprimé de 50 mg de Floxyfral® junior avec le petit déjeuner pendant 7 jours (le dernier jour de prise étant au matin du phénotypage de la session 2, 2 h avant la prise d'oméprazole) Voie d'administration : orale Durée de traitement : 7 jours consécutifs (7 comprimés au total) Dose thérapeutique habituelle : Dose initiale de 50 mg par jour, puis titration jusqu'à 100 mg 1x/j-150 mg 2x/j
 
Rifampicine Spécialité : Rimactan®, caps 300 mg Dosage : 600 mg/j, soit 2 capsules de 300 mg le soir pendant 10 jours (le dernier jour de prise étant le soir de la veille précédent le phénotypage de la session 3) Voie d'administration : orale Durée de traitement : 10 jours consécutifs (20 comprimés au total) Dose thérapeutique habituelle : 600-1200 mg/j selon l'indication

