Each session includes urine collection over a full 24-hour period that will start in the morning of day 0 for session 1, day 10±4d for session 2 and day 26±4d for session 3. It will end in the morning of day 1 for session 1, day 11±4d for session 2 and day 27±4d for session 3. Since most of this part will be performed at home, subjects will be given precise instructions on how to perform it. The last urine stream for each session will be collected in the morning after an overnight fast. Urine will be collected into a 24-hour collection container. This will be stored in a cooler with ice packs and/or a refrigerator.

Immediately after the 24-hour urine collection, venous blood (6 x 6 ml) will be collected and one 10 mg tablet of omeprazole (Antrumups®) administrated. Women will only receive omeprazole after verifying that they are not pregnant (urine test). 2 hours after omeprazole intake, capillary blood sampling (DBS sampling) will be performed. Volunteers will then be free to leave the HUG. Breakfast will be served after capillary blood sampling.

No wash-out period is necessary between the first and second session as fluvoxamine treatment lasts one week, which is sufficient to eliminate omeprazole administered in the first session, as well as its metabolites. Indeed, omeprazole's half-life elimination is generally less than 1 hour, and does not exceed 3 hours in PMs healthy subjects^{45,46}. However, a minimum of six days is necessary between session 2 and session 3. This time gap is required because of the half-life elimination of fluvoxamine being 19,5 hours on average after multiple intakes⁴⁷⁻⁴⁹.

Concerning the second session, participants will be instructed (orally and through reception of an instruction card) to take one 50 mg tablet of fluvoxamine (Floxyfral® junior) every morning for one week (7 doses in total) with the breakfast. If the third visit (session 2) happens exactly 7 days after the second visit (session 1), the drug must be taken during the lunch of session 1 (day 1) in order to have a total of 7 doses of fluvoxamine administrated. Otherwise, the treatment must start one week before the third visit (session 2) and the last dose must be taken 2 hours before omeprazole intake during the day 1 of session 2.

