6.2 Plasma collection

Six tubes of 6 ml venous blood sample (6 x 6 ml) will be drawn during the three sessions and collected in EDTA plasma collection tubes⁷⁴ at the same time as the omeprazole is administrated. Plasma will be obtained after centrifugation of blood samples at 2500 rcf for 10 minutes and aliquots will be conserved at -80°C until analysis. These samples will serve for the untargeted metabolomics analysis of direct plasma and liver-derived extracellular vesicles (liver-specific liquid biopsy) that will be performed by the Laboratory of Forensic Toxicology and Chemistry at the University Centre of Legal Medicine and the Laboratory of Clinical Pharmacology and Toxicology of Geneva University. Fluvoxamine and rifampicin will also be quantified in the Laboratory of Clinical Pharmacology and Toxicology using validated methods.

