8. QUALITY CONTROL AND ASSURANCE

8.1 Data handling and record keeping/archiving

8.1.1 eCRF

The electronic Case Report Form (eCRF) is an investigator file, written for each study subject, which contains data necessary to the progress and the analysis of the study, including safety data.

In this study, the following data will be entered in the eCRF using the browser-based software REDcap :

- Review of inclusion and non-inclusion criteria (check boxes) *
- Demography: gender*, age*
- Concomitant medication(s)*
- weight*, size* and BMI*
- CYP2C19 genotype and phenotype
- For women: date of last menstrual cycle, contraception methods and pregnancy test result at each visit*
- Time of drug intakes*
- Time of venous and capillary blood samplings*
- Time of urine collections*
- SAE resulting in death and SUSARs*

All items followed by an asterisk will be entered directly in the eCRF and will be considered source documents.

Each page will include the subject's and visit's number as well as all the modifications dated and signed by the investigator.

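### The instruction to take fluvoxamine with breakfast on the session 2 morning contradicts the fasting blood draw, so session 2 plasma and vesicle samples may be fed while sessions 1 and 3 are fasted

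*Protocol*

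**What the plan says.** **Dosing.** Section 3.1 has fluvoxamine 50 mg taken "every morning for one week (7 doses in total) with the breakfast", and in a separate sentence places the last dose two hours before omeprazole at session 2. The synopsis (Produit d'étude) joins the two in one sentence: "avec le petit déjeuner pendant 7 jours (le dernier jour de prise étant au matin du phénotypage de la session 2, 2 h avant" the omeprazole dose. In English: with breakfast for seven days, the last of them being the session 2 phenotyping morning.

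**Sampling.** The synopsis (Méthode) describes each session as a 24-hour urine collection followed by "prise de sang veineux (6 x 6 ml) le matin à jeun", that is, fasting venous blood in the morning. Section 3.1 adds: "The last urine stream for each session will be collected in the morning after an overnight fast". It then has venous blood drawn and omeprazole given directly after the urine collection. Section 6.2 confirms that the blood is taken "at the same time as the omeprazole is administrated". On session days, "Breakfast will be served after capillary blood sampling", and that sample comes two hours after omeprazole.

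**Recording.** The eCRF list in section 8.1.1 includes drug intake times and "Time of venous and capillary blood samplings". It has no item for food.

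**The concern.** Someone following the dosing rule eats about two hours before the session 2 blood draw. Someone following the sampling rule does not. The conflict exists at session 2 only: session 1 has no drug beforehand, and the last rifampicin dose is taken the evening before session 3.

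A meal effect would therefore be confounded with fluvoxamine in the session 1 versus session 2 contrast. Within-subject pairing cannot remove a difference present in one session only. Plasma and vesicle features altered by food could be taken for CYP2C19 candidates, and a true candidate could be hidden by a meal effect in the opposite direction.

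The second stage tests only compounds "parmi les composés mis en évidence dans la partie 1" (those flagged in part 1). It can filter out some false candidates, but it recovers a masked one only if session 3 also flags it. Because food intake is not recorded, a fed sample could not be identified afterwards.

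**Working it through.** **Session 2 timeline** (T0 = omeprazole intake; sections 3.1 and 6.2 and the synopsis)

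- T0 − 2 h: last fluvoxamine dose, with breakfast under the dosing rule.
- T0: end of urine collection, venous draw and omeprazole, fasting under the sampling rule.
- T0 + 2 h: capillary sample, then breakfast.

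The dosing rule puts breakfast 2 h before the draw. The sampling rule puts it no earlier than 2 + 2 = 4 h after the dose. The two are incompatible. The option of taking a dose at lunch concerns the first dose only.

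**What is exposed**

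- Plasma and vesicles, session 1 versus 2: up to 30 pairs each in the powered group, 40 each with the 10 poor metabolisers.
- Urine: at most about the last 2 of 24 h, 2/24 = 8% of the collection time.
- Session 1 versus 3, and the baseline genotype comparison: not exposed.

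**How many volunteers would have to eat**

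The protocol states no meal effect, so a multiplicative effect *m* of 1.5, 2 or 3 is assumed for illustration. If a share *p* of the 30 eat, the mean log fold-change shifts by *p* × ln *m*.

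- Unrelated feature reaching the 1.5 cut-off of section 3.2: *p* = ln 1.5 / ln *m* = 1.00, 0.585, 0.369, i.e. 30, 18 or 12 of 30 (rounded up).
- True fold-change of 0.5 pulled above 0.67: *p* = ln(0.67/0.5) / ln *m* = 0.722, 0.422, 0.266, i.e. 22, 13 or 8 of 30.

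**Day counts (minor)**

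Session 1 ends on day 1. The visit windows are day 11 ± 4 (7 to 15) and day 27 ± 4 (23 to 31).

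- Lunch start when session 2 is exactly 7 days after session 1 (day 8): lunch on day 1 plus mornings of days 2 to 8 = 8 doses, against 7 tablets supplied (section 5.2).
- Start one week before session 2, last dose that morning: also 8 doses.
- Latest first doses 9 and 21 days after day 1 (days 10 and 22): session 2 on day 10 + 6 = 16 and session 3 on day 22 + 10 = 32, each one day outside its window.

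A consistent schedule does exist:

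- Earliest: lunch on day 1 plus mornings of days 2 to 7 = 7 doses, session 2 on day 7; rifampicin on evenings 13 to 22, session 3 on day 23. Days 0 to 23 = 24 days.
- Latest: mornings of days 9 to 15 = 7 doses, session 2 on day 15; rifampicin on evenings 21 to 30, session 3 on day 31. Days 0 to 31 = 32 days.

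These match the stated minimum of 24 and maximum of 32 days, so the design is feasible and only the wording is off.

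**The case against.** The fair counter-reading is that fasting is the visit-specific rule and breakfast the general home-dosing rule. In section 3.1 the last dose has its own sentence, without mention of food, and the lunch option shows that the breakfast rule was never literal for every dose. Only the synopsis expressly calls the venous draw fasting; section 3.1 attaches the overnight fast to the last urine, and section 6.2 gives timing alone. A site may well give the last tablet without food. The instruction card and flowchart, which would show what volunteers are told, are not available here.

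These points limit the certainty that any sample will be fed. They do not remove the contradiction, because the synopsis names the session 2 morning within the breakfast instruction. All seven tablets are dispensed for home use (section 5.2), and section 7.2 describes a two-hour visit starting at omeprazole. A dose two hours earlier is thus probably taken at home, where the volunteer's own instruction governs.

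The meal effects used above are assumptions. Section 9.2 also applies FDR-adjusted p-values. If only some volunteers ate, the added within-pair variance would make a purely meal-driven feature less likely to pass, though it would also make a true one harder to detect. The genotype stage and the planned recombinant-enzyme and hepatocyte work would catch some false candidates, but those steps do not retrieve a candidate lost in part 1.

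The day-count errors are small: the seven-dose total and the visit windows are stated clearly enough for a site to work out the intended schedule.

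**Conclusion.** The concern holds. As written, the protocol gives two incompatible instructions for the session 2 morning, and following the dosing one biases part of the primary endpoint. Exposure is up to 30 plasma and 30 vesicle pairs in the powered contrast.

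The actual bias depends on two unknowns: how many volunteers eat, and how strongly a meal shifts each feature. Across the assumed effects of 1.5 to 3, between 12 and 30 volunteers eating would create a false signal at the cut-off, and between 8 and 22 would hide a true halving. The wording conflict is certain; fed samples are possible but not certain. It should be corrected, but it does not undermine the trial as a whole.

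**What to change.** 1. In section 3.1, in the synopsis and on the instruction card, state that the session 2 morning dose is taken fasting, with water only, and that breakfast follows the capillary sample. This sentence resolves the main point.
2. Preferably, add the time of last food before each venous draw to the eCRF, so that lapses can be identified.
3. Correct the day wording: first fluvoxamine dose 6 days before session 2; lunch start only when session 2 is on day 7 (6 days after session 1); latest first doses on study day 9 (fluvoxamine) and study day 21 (rifampicin).

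The cost is amendment wording, one line on the card and one optional eCRF field. No extra volunteers, visits or samples are needed.

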Concerning the third session, participants will also be instructed to take two 300 mg tablets of rifampicin (Rimactan®) every evening for 10 days (10 doses in total) before the fourth visit. This regimen will begin at least 6 days after the third visit (session 2) and the last rifampicin intake will be done at the evening preceding the fourth visit (session 3).

Volunteers will be asked to back empty blisters of the drugs that they took home in order to verify compliance.

The total study duration will not exceed 32 days. Therefore, the first dose of fluvoxamine and rifampicin must be taken, at the latest, 9 days and 21 days after day 1 of session 1, respectively (see study design page 13).

The order of sessions is purposely not randomized due to unnecessity. Indeed, as it is solely a PK study performed on paired samples, there are no possible biases requiring randomization.

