3.4 Study duration for subjects and stopping rules

Apart from the screening session (visit 1), the minimal study duration will be 24 days (day 0-27±4d) including 3 half-days spent in the HUG (visit 2, 3 and 4).

Volunteers will be able to withdraw from the study at any time without any explanation or justification. The data collected up at this moment will be conserved and used unless the volunteer wants its signed informed consent withdrawn. The investigator will also have the possibility to exclude a volunteer from the study for safety reasons or lack of compliance.

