5.2 Packaging, Labelling and Supply

The medications for this study will be purchased from the HUG Pharmacy. They will remain in their original primary packaging (blister packs). A pharmacist from the Division of Clinical Pharmacology and Toxicology will handle the labelling and distribution. Each drug package will be labelled with the product name, dosage form, strength, batch number, expiry date, patient number, and the warning “tenir hors de portée des enfants.” Additionally, the labels will include the protocol number and name, the statement “use only as part of a clinical trial,” and the name of sponsor and principal investigator. For fluvoxamine and rifampicin, healthy subjects will receive the exact number of tablets required for home use (7 tablets for fluvoxamine and 20 tablets for rifampicin) in a labelled ziplock bag.

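### Section 3.1's lunch-start rule for fluvoxamine gives one dose too many, and its latest start days for fluvoxamine and rifampicin overshoot the visit windows by one day

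*Protocol*

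**What the plan says.** All references are to the protocol.

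- **Visit days (section 3.1).** The 24-hour urine collection of session 1 starts on day 0. On when each collection finishes, and hence the visit day: "It will end in the morning of day 1 for session 1, day 11±4d for session 2 and day 27±4d for session 3".
- **Fluvoxamine course.** The synopsis and section 3.1 give 7 once-daily doses. The synopsis places the last one on the session 2 morning: "le dernier jour de prise étant au matin du phénotypage de la session 2, 2 h avant la prise" of omeprazole. Section 5.2 supplies no spare: "healthy subjects will receive the exact number of tablets required for home use (7 tablets for fluvoxamine and 20 tablets for rifampicin").
- **Lunch rule (section 3.1).** "If the third visit (session 2) happens exactly 7 days after the second visit (session 1), the drug must be taken during the lunch". The lunch meant is the one on the day of session 1, and the stated purpose is a total of 7 doses.
- **All other visit days (section 3.1).** "the treatment must start one week before the third visit (session 2) and the last dose must be taken 2 hours before omeprazole intake".
- **Rifampicin (section 3.1).** Ten evening doses, starting at least 6 days after session 2 and ending the evening before session 3.
- **Latest starts (section 3.1).** These are presented as following from the 32-day maximum: "the first dose of fluvoxamine and rifampicin must be taken, at the latest, 9 days and 21 days after day 1 of session 1".
- **Duration.** Synopsis: "Au minimum 24 jours et au maximum 32 jours par volontaire". Section 3.4: "the minimal study duration will be 24 days (day 0-27±4d").

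**The concern.** Seven once-daily doses ending on the morning of a visit must start 6 days before it, not 7. The lunch rule is tied to a 7-day gap, and the two latest starts look like study-day labels written as intervals after day 1. If so, section 3.1 contradicts the protocol's dose count and tablet supply in one place, and its visit windows and duration limit in another.

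These rules govern home dosing before the inhibition and induction sessions, whose intensities the primary endpoint (section 3.2) compares across sessions. A volunteer who starts a day early runs out of tablets the day before session 2. The dose meant to precede the venous sample and the omeprazole test is then missed. A volunteer who starts on the written latest day either has a visit outside its window or takes one dose too few.

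**Working it through.** **Inputs**

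- Session 1 visit: day 1 (section 3.1).
- Session 2 visit, day V: 11 ± 4, so days 7 to 15, which is 15 − 7 + 1 = 9 permitted days.
- Session 3 visit, day W: 27 ± 4, so days 23 to 31.
- Fluvoxamine: 7 doses, the last on the morning of V; 7 tablets supplied (synopsis, sections 3.1 and 5.2).
- Rifampicin: 10 evening doses, the last on the evening of W − 1; first dose at least 6 days after V (section 3.1).

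**Formulas**, with S the day of the first dose

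- Fluvoxamine doses = V − S + 1, so 7 doses require S = V − 6.
- Rifampicin doses = W − S, so 10 doses require S = W − 10.

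**Step 1: figures in the protocol that do reproduce**

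- Minimum duration: days 0 to 23 = 23 − 0 + 1 = 24 days.
- Maximum duration: days 0 to 31 = 31 − 0 + 1 = 32 days.
- Shortest path: V = 7, rifampicin from 7 + 6 = 13, evenings 13 to 22, W = 23.
- Longest path: V = 15, rifampicin from 15 + 6 = 21, evenings 21 to 30, W = 31.

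The windows, the 6-day gap, the dose counts and the durations therefore agree, with days counted in the ordinary way (n days after day d is day d + n).

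**Step 2: lunch rule**

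Exactly 7 days after day 1 is day 8.

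| Session 2 day V | Doses with day 1 lunch (S = 1) | Doses on mornings only (S = 2) |
|---|---|---|
| 7 | 7 − 1 + 1 = 7 | 7 − 2 + 1 = 6 |
| 8 | 8 − 1 + 1 = 8 | 8 − 2 + 1 = 7 |

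For a day 8 visit the mornings alone already give 7, and the compulsory lunch dose makes 8. Only a day 7 visit needs the lunch dose, and the rule does not name that day.

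**Step 3: starting one week before the visit**

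- Read as V − 7: doses = 7 + 1 = 8 on every visit day. For V = 7 the start is day 0, before the baseline samples are complete.
- Read as V − 6: 7 doses, as intended.

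**Step 4: latest starts**

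| | Start as written | Visit day for a full course | Limit | Doses if the window is kept |
|---|---|---|---|---|
| Fluvoxamine | 1 + 9 = day 10 | 10 + 6 = day 16 | day 15 | 15 − 10 + 1 = 6 |
| Rifampicin | 1 + 21 = day 22 | 22 + 10 = day 32 | day 31 | 31 − 22 = 9 |

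With W = 32 the study runs from day 0 to day 32, which is 33 days against 32. The starts that fit are 15 − 6 = day 9 and 31 − 10 = day 21.

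**Step 5: missed-dose scenario**

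If a volunteer with a day 8 visit starts at lunch on day 1, the seventh and last tablet is taken on the morning of day 7. It then precedes omeprazole by about 24 + 2 = 26 hours instead of 2.

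**The case against.** The best defence is inclusive counting. If day 1 counts as the first day, or if 9 and 21 are read as study-day labels, the written figures come out right: a lunch start for a visit on day 7, fluvoxamine by day 9, rifampicin by day 21. The 24-day minimum is itself an inclusive count, and the study-design figure to which section 3.1 refers cannot be seen in the available text. This probably explains how the wording arose, but it does not rescue it. The text says after the second visit and after day 1. The neighbouring 6-day rule for rifampicin matches the windows only with ordinary counting: inclusively, a day 7 session 2 would allow a start on day 12 and session 3 on day 12 + 10 = 22, before the window opens. Section 3.1 would need two conventions, with no sign of which applies where.

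Other points stand in part:

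- The clause for all other visit days does reach day 7. Read as V − 6, it gives the right start there, and the synopsis allows a lunch start. The gap at day 7 therefore lies in the lunch rule alone and bites only if one week is read as 7 days.
- The latest starts do not conflict with the dose count or tablet supply as such. Their conflict is with the windows and the duration limit, unless a dose is dropped to stay within the window.
- The last-dose rule, the 7-dose total and the tablet count are explicit, intake times are recorded, and plasma drug levels are measured, so staff may well catch a slip.
- The effect on the primary endpoint is probably small. A final tablet 2 hours before omeprazole touches only the end of the urine collection, and 9 rifampicin doses still exceed the 7 days that section 5.1.3 requires for full induction.

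These points limit the likely harm; they do not remove the contradiction.

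**Conclusion.** The point holds. With ordinary day counting, each of the three rules is one day off the protocol's own figures:

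- the lunch rule gives 8 doses against 7 tablets, on 1 of the 9 permitted session 2 days;
- the latest fluvoxamine start puts session 2 on day 16 against a limit of 15;
- the latest rifampicin start puts session 3 on day 32 against a limit of 31, and the total at 33 days against 32.

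The general instruction to start one week before session 2 is ambiguous by the same day. The missed pre-omeprazole dose is a possible consequence, arising only if the start wording is followed over the last-dose rule. No sample size, analysis, dose total or supply is affected. Because these are working instructions for home dosing, they should be corrected rather than left to interpretation. The instruction card and the design figure were not available to check.

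**What to change.** In section 3.1:

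1. State that fluvoxamine starts 6 days before the session 2 visit, and never before the session 1 samples have been taken.
2. Restrict the lunch start to a session 2 visit on day 7, that is, 6 days after session 1.
3. Give the latest first doses as study day 9 for fluvoxamine and study day 21 for rifampicin (8 and 20 days after day 1).
4. Use the same day count on the volunteers' instruction card, and check that the design figure agrees.

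As a check, fluvoxamine on days 9 to 15 is 7 doses with session 2 on day 15; rifampicin on evenings 21 to 30 is 10 doses with session 3 on day 31; days 0 to 31 make 32 days.

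The cost is a wording correction and a check of the card. No extra visits, tablets or volunteers are needed.
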